5.1.2.2.2 Safety

Safety profile will be described after booster vaccination with CYD dengue vaccine.

The safety analysis will address the number and percentage of subjects with injection site reactions (pain, erythema, and swelling) from D0 and D07, solicited systemic reactions (fever, headache, malaise, myalgia, and asthenia) from D0 to D14, unsolicited AEs until D28, non-serious AESIs (hypersensitivity/allergic reactions) from D0 to D07, and unsolicited immediate systemic event occurring within 30 minutes after a booster CYD dengue vaccine dose. Solicited injection site reactions or solicited systemic reactions will be described according to time of onset, number of days of occurrence, action taken, and intensity.

Unsolicited AEs or non-serious AESIs will be described according to nature (MedDRA SOC, and PT), time to onset, duration, intensity, action taken, and relationship to vaccination.

Unsolicited immediate systemic events will be described according to nature (MedDRA SOC, and PT) and relationship to vaccination.

The number and percentage of subjects with SAEs, including serious AESIs will be described according to nature (MedDRA SOC, and PT), seriousness criteria, outcome, and relationship to vaccination throughout the trial.

All AEs leading to study termination will be described according to nature (MedDRA SOC, and PT) and relationship to vaccination.

The exact binomial distribution (Clopper-Pearson method) for proportions will be used in calculations of the 95% CIs.

Detection of hospitalized virologically-confirmed dengue cases

The number and percentage of subjects with a hospitalized virologically-confirmed dengue cases occurring at any time throughout the trial after the injection will be described using safety analysis set (SafAS).

The 95% CIs for percentages will be calculated using the exact binomial distribution (Clopper-Pearson's method).

5.1.3 Statistical Methods for Observational Objectives

5.1.3.1 Hypotheses

There are no hypotheses.

5.1.3.2 Statistical Methods

5.1.3.2.1 All of the analyses in the AIT subset

The analyses for AIT subset are based on the following:

Dengue PRNT (at V02 and V03): neutralizing Ab levels against each of the four parental dengue virus strains as determined by PRNT.

CMI responses (at V01, V02, V03, V04, and V06):

- Cytokine secreting CD4 and CD8 T cells count (at V01, V04, and V06)

Note: The raw individual results will not be directly described in the analysis: the results of all stimulations will be corrected with the corresponding medium result. The detailed calculation is:

For envelope (ENV) CYD 1, ENV CYD 2, ENV CYD 3, ENV CYD 4, NS3 peptide pools from YF 17D and DEN, and positive control, the medium (MED) = value of the negative control medium.

Therefore, the following corrected endpoints will be used:

- Before vaccination: $X_{D0} - MED_{D0}$ where X is the value of ENV CYD 1, ENV CYD 2, ENV CYD 3, ENV CYD 4, positive control or NS3 peptide pools from YF 17D and DEN, etc.
- 28 days after vaccination: $X_{D28} - MED_{D28}$,
- 12 months after vaccination: $X_{M12} - MED_{M12}$,
- Change from baseline endpoints (ratio): $(X_{D28} - MED_{D28}) / (X_{D0} - MED_{D0})$ and $(X_{M12} - MED_{M12}) / (X_{D0} - MED_{D0})$.
- Change from D28 endpoints (ratio): $(X_{M12} - MED_{M12}) / (X_{D28} - MED_{D28})$.
- T cell subpopulation (naïve, effector, central and terminally differentiated memory T cells) count (at V01, V04, and V06)

Note: Naïve T cells are defined as CD45RA⁺ and CCR7⁺, effector memory T cells defined as CD45RA⁻ and CCR7⁻, central memory T cells defined as CD45RA⁻ and CCR7⁺, and terminally differentiated memory T cells as CD45RA⁺ and CCR7⁻.

No corrected value will be used for the subpopulation analyses. Only the raw values of the medium, ENV CYD1, ENV CYD 2, ENV CYD 3, ENV CYD 4, positive control or NS3 peptide pools from YF 17D and DEN will be summarized.

- Cytotoxic T cell effector markers (at V01, V04, and V06)

Note: The functional markers are IFN γ , TNF α , IL-2, MIP-1 β and CD107a for CD3⁺ CD8⁺ T cells, and have one more marker CD154 for CD3⁺ CD4⁺ T cells. The cytotoxic T cell will be also summarized for activated cells, simple positive cells, double positive cells, triple positive cells and more than triple positive cells. The definition for different cells are:

- Activated cells: Positive for at least one of the following markers IFN γ /TNF α /IL-2/MIP-1 β /CD107a for CD3⁺ CD8⁺ cells and IFN γ /TNF α /IL-2/MIP-1 β /CD107a/CD154 for CD3⁺ CD4⁺ cells
- Simple positive cells: Activated cells which express 1 of the following markers IFN γ /TNF α /IL-2/MIP-1 β /CD107a for CD3⁺ CD8⁺ cells and IFN γ /TNF α /IL-2/MIP-1 β /CD107a/CD154 for CD3⁺ CD4⁺ cells
- Double positive cells: Activated cells which express 2 of the following markers IFN γ /TNF α /IL-2/MIP-1 β /CD107a for CD3⁺ CD8⁺ cells and IFN γ /TNF α /IL-2/MIP-1 β /CD107a/CD154 for CD3⁺ CD4⁺ cells
- Triple positive cells: Activated cells which express 3 of the following markers IFN γ /TNF α /IL-2/MIP-1 β /CD107a for CD3⁺ CD8⁺ cells and IFN γ /TNF α /IL-2/MIP-1 β /CD107a/CD154 for CD3⁺ CD4⁺ cells
- More than triple positive cells: Activated cells which express 3 of the following markers IFN γ /TNF α /IL-2/MIP-1 β /CD107a for CD3⁺ CD8⁺ cells and IFN γ /TNF α /IL-2/MIP-1 β /CD107a/CD154 for CD3⁺ CD4⁺ cells

In addition, the number of responders to the ICS test by stimulation will be computed. To be considered as responders the two following conditions must be filled:

$$\frac{X_{post-booster} - MED_{post-booster}}{X_{D0} - MED_{D0}} \geq 2$$

$$[X_{post-booster} - MED_{post-booster}] - [X_{D0} - MED_{D0}] \geq 0.05\%$$

The post-booster visits here are D28 and M12.

- Ex vivo B cells (plasmablast) count (measured by ELISPOT, at V01, V02, and V03)

Number of antibody secreting cells (ASC) for each of the four specific parental dengue virus strains IgG and the total IgG will be summarized.

- Memory B cells count (measured by ELISPOT, at V01, V04, and V06)

Note: Number of antibody secreting cells (ASC) for each of the four specific parental dengue virus strains IgG and the total IgG will be summarized. In addition, for each of the four specific parental dengue virus strains IgG, the ratio will be also calculated. The ratio (%) can be obtained by:

$$\text{Ratio} = \frac{\text{ASC for CYD1/2/3/4 IgG}}{\text{ASC for Total IgG}} \times 100\%$$

Ab specificity and affinity maturation (at V01, V02, V03, and V04):

- The neutralizing Abs in the depleted, BSA-control depleted sera and whether the response is homotypic for each of the four parental dengue virus strains will be assessed (at V01, V02, V03, and V04).

Note: Undepleted is defined as BSA-control depleted and depleted is DENV depleted. Homotypic response is defined as a neutralizing antibody titer above 20 (1/dil) following DENV depletion.

- Serotype-specific affinity (K_A , nM^{-1}) and Ab concentration ($\mu\text{g/mL}$) for each of the four parental dengue virus strains will be measured (at V01 and V04).

Note: K_D (nM) will be collected from the lab and summarized in the final report, where $K_A = 1/K_D$.

All the analyses will be descriptive.

- For categorical data, the number and percentage of subjects above or equal to the LLOD, and the 95% CI of the percentage of the subjects.
- For continuous data, Log10: mean and standard deviation; geometric mean, 95% CI of the geometric mean and quartiles, minimum and maximum value.

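### The ICS responder rule cannot be met when the medium-corrected baseline is negative, and its ratio is undefined when that baseline is zero

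*SAP*

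**What the plan says.** SAP 5.1.3.2.1 states that for the cytokine-secreting T-cell counts "the results of all stimulations will be corrected with the corresponding medium result". The correction is a plain subtraction of the negative-control medium value at the same visit, with no truncation. Ratios of the corrected values are then formed: D28 to D0, M12 to D0 and M12 to D28.

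Response is counted separately for each stimulation: "In addition, the number of responders to the ICS test by stimulation will be computed". The rule is conjunctive: "To be considered as responders the two following conditions must be filled". The first condition is a corrected post-booster to corrected D0 ratio of at least 2. The second is a corrected post-booster value at least 0.05% above the corrected D0 value. On timing, "The post-booster visits here are D28 and M12".

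SAP Table 5.1 and the end of 5.1.3.2.1 also call for log10 means and geometric means, and Table 5.1 applies the geometric means to corrected values. The T-cell subpopulation summaries are exempt: "No corrected value will be used for the subpopulation analyses".

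**The concern.** Subtracting a background reading gives a negative result whenever the stimulated well reads below its own medium control, and the SAP neither excludes nor truncates such results. A ratio with a negative or zero denominator does not measure a fold-rise. A subject with no detectable response before the booster and a clear one afterwards is the case the responder count should capture, and it is the case the rule can reject.

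Responder percentages for the affected stimulations may therefore be too low. The change ratios and geometric means may rest on the positive values only, without a statement to that effect. Because no rule is written, whoever programs the tables has to choose one, and SAP 5.4 unblinds the data for the D28 and 1-year analyses.

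**Working it through.** **Inputs.** All definitions come from SAP 5.1.3.2.1. For one stimulation and one post-booster visit:

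- b = X_D0 - MED_D0
- p = X_post - MED_post, with post = D28 or M12
- responder if p/b >= 2 and p - b >= 0.05%

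**Algebra.**

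- b > 0: p/b >= 2 means p >= 2b. The rule works.
- b < 0: multiplying by b reverses the inequality, so p/b >= 2 means p <= 2b. Then p - b <= b < 0, which contradicts p - b >= 0.05%.
- b = 0: p/b is a division by zero.

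**Examples.**

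- b = +0.01%, p = +0.30%: ratio 30, difference 0.29%, responder.
- b = -0.01%, p = +0.30%: ratio -30, difference 0.31%, non-responder.
- b = -0.01%, p = -0.03%: ratio 3, difference -0.02%. The ratio condition is met by a fall.

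**Grid check** (b from -0.300% to 0.300%, p from -0.700% to 3.000%, step 0.001%). With b < 0, 930,450 pairs meet the difference condition, 120,000 meet the ratio condition and 0 meet both. With b > 0, 808,775 of the 840,150 pairs with a sufficient rise meet both.

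**Search for a rescuing rule.**

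- SAP 4.4.1.1 substitutes for values below the LLOQ in a denominator, but for titers, and no ICS limit is given to which it could apply.
- The LLODs in SAP 4.3.1.2 are for antibody specificity and affinity.
- The AIT text says "For categorical data, the number and percentage of subjects above or equal to the LLOD", but no LLOD is given for ICS.
- SAP 5.3.1 lets the laboratory exclude aberrant values without defining them.
- Protocol 11.2 refers to laboratory procedures that are not in the documents.
- Protocol 9.3.1.2.3 describes the ICS assay and gives no responder rule.

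**Possible size.** The documents give no ICS distributions, so these are assumptions: normal, independent errors with the same SD at both visits, in % of cells, 2,000,000 draws per scenario. Each cell compares the rule as written with the replacement rule given in the fix.

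| Baseline mean, SD | b <= 0 | True rise 0.15% | True rise 0.07% | No true rise |
|---|---|---|---|---|
| 0, 0.02 | 50% | 50% vs >99% | 29% vs 71% | 0.1% vs 0.4% |
| 0, 0.03 | 50% | 48.5% vs 98.5% | 23% vs 60% | 0.7% vs 3.1% |
| 0.02, 0.02 | 16% | 84% vs >99% | 60% vs 75% | 0.9% vs 2.0% |
| 0.05, 0.03 | 5% | 88% vs 93% | 55% vs 59% | 8.5% vs 10.9% |
| 0.05, 0.02 | 0.6% | 98.1% vs 98.7% | 65% vs 66% | 3.4% vs 3.8% |

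No draw with b < 0 was a responder under the rule as written. The two rules never disagreed when b > 0. With a correlation of 0.5 between visits, the first two rows at a rise of 0.15% give 50% vs >99% and 50% vs 99.8%.

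**Chance that the gap in the rule is met at all.** For one stimulation, the probability that at least one of 45 booster subjects has no usable ratio is 1 - 0.99^45 = 0.36 if 1% have b <= 0, and 1 - 0.95^45 = 0.90 if 5% do.

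**The case against.** The algebra is not in dispute; the objections concern weight and remedy.

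- **Reach.** The rule feeds a descriptive additional endpoint in 60 subjects, with no hypotheses. This stands and limits the severity.
- **Frequency.** The largest gaps assume a mean corrected baseline of zero. All subjects had received three CYD doses and live where dengue circulates, so higher baselines are plausible, and with a mean of 0.05% the loss at a 0.15% rise is about 5 points or less. This stands: the simulations are not evidence about this trial.
- **Direction.** D0 blood is drawn before injection and treatment is randomised, so non-positive baselines should be balanced between groups. The rule can dilute a difference in responder percentages but does not create a booster effect. This also stands, although dilution is still an error in what is reported.
- **Other output.** Quartiles, minimum and maximum remain valid for zero or negative values, so a rise stays visible in the distributions. True, but that does not repair the responder counts, ratios or geometric means.
- **The remedy is one of several.** For b < 0 the replacement requires p >= 0.05%, which is stricter than p - b >= 0.05%. A change from -0.04% to +0.02% is a rise of 0.06% and would still not count. With baseline mean 0 and a true rise of 0.07%, about 5% to 8% of subjects fall in this position. A positive floor, or the difference condition alone, are alternatives. The choice is a judgement; the need for a stated rule is not.

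**Conclusion.** The rule is wrong as written for every negative corrected baseline and undefined at zero, whatever the stimulation, the visit or the size of the rise. This follows from the two stated conditions and needs no assumption. It works by stimulation, so a subject blocked for one can still respond to another. The same values leave the change ratios and the log10 and geometric-mean summaries of corrected data undefined or without meaning.

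How much this matters depends on how often b <= 0 occurs, which the documents do not say. Under the assumptions above, the loss of responders at a 0.15% rise runs from 0.6 to about 50 percentage points. Primary, secondary and safety results are untouched. It is a point to consider and correct, and it does not threaten the trial's conclusions.

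**What to change.** In SAP 5.1.3.2.1, set b0 = max(b, 0) and class a subject as a responder to a stimulation if p >= 2 x b0 and p - b0 >= 0.05%. This leaves every classification with b > 0 unchanged, needs no assay limit, and reduces to p >= 0.05% when b <= 0.

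For the ratio, log10 and geometric-mean summaries of corrected values only, pre-specify one positive floor supplied by the laboratory that runs ICS, and report the number of floored values by group and visit.

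As an editorial correction in the same section, "More than triple positive cells: Activated cells which express 3 of the following markers" repeats the triple-positive definition; it should read at least 4 of the listed markers.

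The cost is a few sentences and minor programming. False responders increase by at most 2.4 percentage points in the scenarios tried (0.7% to 3.1%, and 8.5% to 10.9%). With baseline mean 0 that is a more than fourfold relative increase from a very low rate. The floored summaries will depend on the floor chosen; the responder rule will not.

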5.1.3.2.2 Analysis adjusting for baseline neutralizing Ab levels

Analysis of covariance (ANCOVA) will be used to compare the post-booster mean response of neutralizing Ab levels against each dengue virus serotype of Groups 1 and 2 adjusting for the baseline neutralizing Ab levels against each dengue virus serotype based on the least squares means (LSMEANS).

For each serotype, the following model will be considered:

$$\text{Log}_{10} \text{ titer}_i = \text{log}_{10} \text{ baseline}_i + \text{group}_i$$

Where:

titer_i is the post-booster titer value for each subject

baseline_i is pre-booster titer value for each subject

group_i is Group 1 or Group 2 for each subject

Before applying the above ANCOVA model, the interaction between the pre-booster titer value and the group will be assessed using the following model:

$$\text{Log}_{10} \text{ titer}_i = \text{log}_{10} \text{ baseline}_i + \text{group}_i + \text{log}_{10} \text{ baseline}_i \times \text{group}_i$$

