Trial Design and Methodology:	
This will be a multi-center, observer-blind, randomized, placebo-controlled Phase II trial conducted in Singapore to assess i) the non-inferiority of the immune response induced by a booster injection of a tetravalent dengue vaccine versus that induced by the third injection of the 3-dose schedule of the same vaccine received 5 years (or more) earlier in healthy subject from the CYD28 trial; ii) to evaluate the safety and antibody persistence of the booster injection up to 2 years.
 
Subjects will be randomized into Groups 1 and 2 in a 3:1 ratio and will receive either the CYD dengue vaccine as a booster or a placebo.
 
A total of 260 subjects aged 9 to 45 years on the day of first vaccination of the study vaccine in CYD28 are planned to be recruited into the following 2 groups.
 
  
 	Vaccination in CYD28	CYD63	
 
 N	Product to be injected	
   
 Group 1	CYD1/CYD2/CYD3*	195	CYD dengue vaccine booster	
 
 Group 2	CYD1/CYD2/CYD3*	65	Placebo	
  
 
* CYD dengue vaccine dose 1, dose 2, and dose 3
 
An interactive voice response system/interactive web response system (IVRS/IWRS) will be used to assign treatment group and subject number at each clinical site, with stratification for age (9 to 17 years, and 18 to 45 years, on the day of first injection in CYD28) and trial center.
 
At the first visit, each subject will receive a single dose of the CYD dengue vaccine booster or a placebo. Blood samples will be collected at baseline (immediately prior to injection), at 28 days, 6 months, 1 year and 2 years post-injection for assessing neutralizing antibody (Ab) titers against each of the four parental dengue virus strains. A subset of 60 subjects in Group 1 and Group 2 (45 and 15 subjects, respectively) will provide additional blood samples at baseline and at 7, 14, 28 days and 1 year post-injection. Depending on the time points, these blood samples will be used for
		Vaccination in CYD28	CYD63		N	Product to be injected	Group 1	CYD1/CYD2/CYD3*	195	CYD dengue vaccine booster	Group 2	CYD1/CYD2/CYD3*	65	Placebo
	Vaccination in CYD28			CYD63											
		N	Product to be injected												

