2.3 Additional Objectives

Only for the additional immunological tests (AIT) subset

- 1) To describe dengue neutralizing Ab levels (exploration of the Ab response's kinetics), Ab specificity and affinity maturation post-booster or placebo injection
- 2) To describe CMI responses post-booster or placebo injection.

In all subjects

- 3) To assess post-booster neutralizing Ab levels against each dengue virus serotype while controlling for baseline neutralizing Ab levels against each dengue virus serotype

The endpoints for the additional objectives are presented in [Section 9.3.1.1](#).

3 Investigators and Trial Organization

This trial will be conducted in 3 centers in Singapore. Details of the trial centers and the Investigators at each center are provided in the “List of Investigators and Centers Involved in the Trial” document.

An Independent Data Monitoring Committee (IDMC) will be involved in the regular review of hospitalized virologically-confirmed dengue (VCD) cases^a, including assessment of severity. Additionally, any related serious adverse event (SAE) or death or serious adverse events of special interest (AESIs) will be promptly reviewed by the IDMC.

An internal safety management team (SMT) will perform a blinded safety analysis on safety data after vaccination.

The laboratories involved in this study will be:

^a Hospitalized suspected dengue disease is defined as an acute febrile illness with diagnosis of dengue requiring hospitalization (with bed attribution). In such cases, one unplanned blood sample will be collected for virological confirmation: an acute sample (within the first 5 days after fever onset). A suspected hospitalized dengue case will be considered a serious VCD case if there is a detection of wild type (WT) dengue virus by NS1 antigen ELISA and/or wild-type dengue RT-PCR.

- Sanofi Pasteur Global Clinical Immunology (GCI), Swiftwater, Pennsylvania, USA or outsourced laboratory under the management of GCI: Neutralizing Ab titration and virological confirmation of dengue
- Sanofi Pasteur Research & Non Clinical Safety department, Marcy L'Etoile, France: CMI response
- Sanofi Pasteur VaxDesign, Orlando, Florida, USA: Ab specificity and affinity maturation and associated statistical analysis

Biostatistics, data management, monitoring, and medical writing will be either subcontracted to a CRO or performed in-house by the Sponsor.

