6.5 Randomization and Allocation Procedures

Each subject who meets the inclusion/exclusion criteria and signs (along with the subject's parent(s) / legally acceptable representative(s) for subjects aged < 21 years) the ICF will be randomly assigned to one of the 2 groups via an IVRS/IWRS, according to a 3:1 ratio (3 subjects included in the CYD dengue vaccine group for 1 subject included in the control group).

Site staff will call or connect to the IVRS/IWRS, enter identification and security information, and confirm a minimal amount of data in response to IVRS/IWRS prompts. The IVRS/IWRS will then state the vaccine assignment (code number). Subject numbers will be recorded on the CRFs and will not be reassigned for any reason. The full detailed procedures for randomization are described in the Operating Guidelines.

The first 60 randomized subjects from two specific sites (30 subjects per site) will be selected for the AIT subset.

Subject numbers will be 8 digits long, with a 3-digit center identifier and a 5-digit subject identifier. The first digit of the subject identifier will be a pre-defined figure (0 or 1); "1" will be used for subjects assigned to AIT subset and "0" for all other subjects. The second digit of the subject identifier will be a pre-defined figure (0 or 1); "1" will be used for subjects aged 18 to 45 years and "0" for subjects aged 9 to 17 years. For example, subject 001-11001 will be the first randomized to the AIT subject with age of 18 to 45 years from center 1.

Subject numbers used in CYD28 will be captured on the CRFs.

Randomization will be performed with permuted block method with stratification by site and age group.

A double randomization system will be used, this implies that the subject treatment allocation will be separated from doses dispensing. Each dose will have both a code number and a dose number. The code number will be used by the IVRS/IWRS while the dose number will be entered in the CRF. The unique dose numbers will be defined according to a random list to ensure that dose numbers cannot be used to distinguish between treatment groups.

Subject numbers should not be reassigned for any reason. The Clinical and Medical Quality Operations department at Sanofi Pasteur will hold the randomization codes in a secured location.

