12.1.3 Statistical Methods for Additional Objectives

There are no hypotheses. All of the analyses in the AIT subset will be descriptive.

- For categorical data, the number and percentage of subjects above or equal to the lower limit of detection (LLOD), and the 95% CI of the percentage of the subjects.
- For continuous data, Log10: mean and standard deviation; geometric mean, 95% CI of the geometric mean and quartiles, minimum and maximum value.

For the last additional objective, analysis of covariance (ANCOVA) will be used to compare the post booster mean response of neutralizing Ab levels against each dengue virus serotype of two groups controlling for the baseline neutralizing Ab levels against each dengue virus serotype. Further details regarding the ANCOVA model will be outlined in the SAP.

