2.3 Additional Objectives

Only for the additional immunological tests (AIT) subset

- 1) To describe dengue neutralizing Ab levels (exploration of the Ab response's kinetics), Ab specificity and affinity maturation post-booster or placebo injection
- 2) To describe cell mediated immunity (CMI) responses post-booster or placebo injection.

^a If the planned sample size is not achieved, the analysis may be descriptive.

In all subjects

- 3) To assess post-booster neutralizing Ab levels against each dengue virus serotype while controlling for baseline neutralizing Ab levels against each dengue virus serotype

3 Description of the Overall Trial Design and Plan

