4.4.5.2 Age group

The age group code (“9 to 17 years of age” or “18 to 45 years of age” on the day of first injection in CYD28) is a part of the subject number. Nevertheless subjects with a wrong identifier due to misclassification at the time of randomization will be considered in their real strata of age at the time of analysis, based on the age definition in [Section 4.4.5.1](#).

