5.5 Determination of Sample Size and Power Calculation

There will be 195 subjects in Group 1, 65 subjects in Group 2. Assuming that 10% of subjects from each group will not provide valid immunogenicity results, a total of 176 and 59 evaluable subjects is anticipated for Groups 1 and 2, respectively. With 176 evaluable subjects, the probability of observing at least 1 AE with true incidence of 1.7% is approximately 95%.

Sample size for the primary endpoint (only for Group 1 subjects) was estimated to demonstrate non-inferiority of a CYD dengue vaccine booster compared to the third CYD dengue vaccine dose in subjects from CYD28 trial in terms of GMTR.

With 176 evaluable subjects in Group 1, for each serotype, there is 80.2% overall power (see [Table 5.2](#)) using paired t-test to reject the 4 individual null hypotheses simultaneously; calculation assumed a non-inferiority margin (δ) =2, one-sided type I error =0.025 and correlation between the responses PD3 and post-booster dose of the same serotype in the same subject = 0.6.

Table 5.2: Power/Sample size calculation summary table for primary endpoint (only for Group 1 subjects)

Component (Antigen)	Standard deviation (log 10)	Non-Inferiority Definition	Power for N=176
Serotype 1	(sd1=0.77,sd2=1.54)	> 1/2	0.892
Serotype 2	(sd1=0.74,sd2=1.48)	> 1/2	0.914
Serotype 3	(sd1=0.59,sd2=1.18)	> 1/2	0.970
Serotype 4	(sd1=0.53,sd2=1.06)	> 1/2	0.996
Overall			0.802

The standard deviation for PD3 (sd1) is based on 28-day PD3 standard deviations of titers from CYD28. The standard deviation for post-booster (sd2) is estimated as two folds of the sd1 for each serotype.

Since 4 individual null hypotheses should be rejected simultaneously to reject the overall null hypothesis, so no multiplicity adjustment for alpha is necessary.

A 3:1 randomization ratio between Group 1 and Group 2 was chosen, so there will be 195 and 65 subjects enrolled in Group 1 and Group 2, respectively.

For the assessment of CMI, additional neutralizing Ab titers (for exploration of the Ab response's kinetics), Ab specificity and affinity maturation, the AIT subset will include the first 60 randomized subjects from two specific sites (30 subjects per site): 45 subjects in Group 1 and 15 subjects in Group 2.

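### The baseline-adjusted booster-versus-placebo ANCOVA omits site and age group, the two randomisation strata; its standard error is overstated if they predict post-booster titer beyond baseline titer

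*SAP*

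**What the plan says.** **Randomisation.** Protocol section 6.5: "Randomization will be performed with permuted block method with stratification by site and age group". The synopsis gives the age bands: "stratification for age (9 to 17 years, and 18 to 45 years, on the day of first injection in CYD28) and trial center". Protocol section 3: "This trial will be conducted in 3 centers in Singapore". Allocation is 3:1.

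**Model.** Protocol section 12.1.3 calls for an ANCOVA of post-booster titer controlling for baseline and leaves the rest to the SAP: "Further details regarding the ANCOVA model will be outlined in the SAP". SAP section 5.1.3.2.2 compares "Groups 1 and 2 adjusting for the baseline neutralizing Ab levels against each dengue virus serotype based on the least squares means (LSMEANS". It writes out two models per serotype. One has log10 baseline titer and group. The other, fitted beforehand as a check, adds their interaction. Neither contains site or age group. The section asks for least squares means but specifies no confidence interval for the adjusted contrast. It names no visit for the post-booster titer; day 28 is assumed here.

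**Elsewhere.** The other booster-placebo comparison is a two-sample t interval for the ratio of GMTs, with no covariate (Protocol section 12.1.2.2.1, SAP section 5.1.2.2.2.1). Age group otherwise appears only in the subgroup tables of SAP section 5.1.4, and site enters no analysis model. For age, SAP section 4.4.5.2 says that subjects with "misclassification at the time of randomization will be considered in their real strata of age at the time of analysis".

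**Status.** The ANCOVA serves the third additional objective in SAP section 2.3: "To assess post-booster neutralizing Ab levels against each dengue virus serotype while controlling for baseline neutralizing Ab levels against each dengue virus serotype". SAP section 5.1.3.1 attaches no hypotheses to it.

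**The concern.** Stratified blocks balance site and age group between the arms, so these factors add little to the chance variation of the booster-placebo difference. A model without them still counts whatever variance they explain as residual noise. Its standard error then describes a less balanced design than the one run, and a nominal 95% interval covers more often than 95%.

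What is at stake is the width of one interval per serotype. The contrast is still worth getting right: it is the only baseline-adjusted model that uses the concurrent randomised control, and only about 59 placebo subjects are expected to be evaluable. The primary and superiority tests compare Group 1 with its own post-dose-3 titers from CYD28.

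**Working it through.** **1. The plan's own figure.** The documents give no precision or power for the ANCOVA. Their only power figure is for the paired primary test (SAP section 5.5). With SD of the difference = √(sd1² + sd2² − 2·0.6·sd1·sd2), N = 176, log10(2) = 0.301 and one-sided alpha 0.025, the SDs are 1.2416, 1.1932, 0.9513 and 0.8546. The powers are 0.8923, 0.9144, 0.9866 and 0.9964, with product 0.8021 against the stated 0.802. Serotype 3 is printed as 0.970, but the stated overall figure fits 0.987. None of this bears on the ANCOVA.

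**2. Inputs for the ANCOVA.** 176 and 59 evaluable subjects (SAP section 5.5), total 235. The planned model has 235 − 3 = 232 residual df. Site (2 df) and age group (1 df) leave 229. R is the share of the planned model's residual variance that the strata explain, that is, beyond baseline titer. The documents give no value, so R = 0, 5, 10 and 20% are assumed.

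**3. CI width.** Half-width on the log10 scale = t × s × √(1/176 + 1/59) = t × s × 0.1504, where s is the residual SD. Fitting the strata multiplies s by √(1 − R), so

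width ratio = √(1 − R) × t(0.975, 229)/t(0.975, 232) = √(1 − R) × 1.9704/1.9702.

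**4. Coverage of the planned interval.** If the strata are exactly balanced, the planned half-width is too long by 1/√(1 − R). Coverage is then the probability that |t| on 229 df is below 1.9702/√(1 − R).

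| R (assumed) | Width ratio | Coverage as planned, formula | Coverage as planned, simulated | Coverage with strata, simulated |
|---|---|---|---|---|
| 0% | 1.000 | 95.0% | 94.8-95.4% | 94.8-95.4% |
| 5% | 0.975 | 95.6% | 95.0-96.0% | 94.4-95.4% |
| 10% | 0.949 | 96.1% | 95.8-96.5% | 94.9-95.4% |
| 20% | 0.894 | 97.1% | 97.0-97.4% | 95.0-95.3% |

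Two simulation set-ups used stratified 3:1 permuted blocks over 3 sites × 2 age groups. One had 260 subjects, equal stratum shares, blocks of 4 or 8, 9.6% missing at random and 10,000 runs per cell. The other had 235 subjects, site shares of 40/35/25%, blocks of 4 and 4,000 runs per cell. Shares, block sizes and missingness pattern are assumptions. Simulated width ratios were 1.000-1.001, 0.975, 0.949-0.950 and 0.894-0.895.

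**5. The estimate itself.** In the first set-up bias was at most 0.004 SD in every cell. The empirical SD of the group estimate fell by at most 1.7% when the strata were fitted (R = 20%, blocks of 8). In the second set-up it was 0.1516 without and 0.1513 with the strata at R = 20%.

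**6. Strata acting only through baseline titer.** The simulated width ratio was 1.001: no gain.

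**7. Scale.** No residual SD is given. Taking s = 0.77 log10 as an example, the half-width is 1.9702 × 0.77 × 0.1504 = 0.228, a factor of ×/÷ 1.69 around the GMT ratio. With the strata it is 1.67, 1.65 or 1.60 at R = 5, 10 or 20%. With s = 1.54 it goes from 2.86 to 2.79, 2.71 or 2.56.

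**The case against.** The best case against acting is that this is small, conditional and on the safe side. Baseline titer is already in the model and may carry most of what site and age predict. The documents offer no evidence of a remaining stratum effect, so every R above zero is assumed. At R = 5% the change in coverage is barely visible. The objective is descriptive and no decision rests on it. The age-group tables in SAP section 5.1.4 already let a reader look at age. Finally, SAP section 5.1.3.2.2 specifies no interval for the contrast, so a criticism of its width is partly inferred.

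Most of this stands, and it makes the point minor. It does not justify the omission. Subgroup tables are not adjustment, the missing interval is itself a reason to add wording, and the cost is close to nil even at R = 0.

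Three stronger readings should be resisted:

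- **Extra subjects.** A reader might turn the narrower interval into a sample-size gain. At R = 20%, 235/0.8945² − 235 ≈ 59. That treats the removal of an overstated standard error as new information. The simulated fall in the estimate's true spread (ratio 0.983 to 0.985) would be worth only 235/0.985² − 235 ≈ 7 to 235/0.983² − 235 ≈ 8.
- **Bias or false positives.** Leaving out balanced strata does neither; the error is conservative.
- **A 0.7% cost.** The usual formula for covariates that are not balanced by design includes √(230/227) = 1.0066, a charge for chance imbalance. Stratification has already removed that imbalance, and the simulated cost at R = 0 is about 0.1%.

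**Conclusion.** The point holds as a minor, free improvement. Both models in SAP section 5.1.3.2.2 leave out the two factors that the randomisation is stratified by, and nothing else in either document supplies them. The consequence depends on one unknown, the residual variance that site and age group explain beyond baseline titer. Over an assumed 0 to 20%, the planned interval runs from correctly sized to about 12% too wide (1/0.895 = 1.12), with coverage from 95% to about 97%. The gain from fitting the strata is a correctly sized interval, not a different or materially more precise estimate, and there is none if the strata act only through baseline. The figures assume 176 and 59 evaluable subjects and loss unrelated to titer. A reader might infer that the trial's main conclusions are in doubt. They are not: the primary non-inferiority and first secondary superiority tests are paired within Group 1 and do not use this model.

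**What to change.** In SAP section 5.1.3.2.2:

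- Add age group (9-17, 18-45 years) and site (3 centers) as fixed effects to both the ANCOVA and the interaction model: log10 titer = log10 baseline + group + age group + site, plus baseline × group in the second. Use the actual age stratum, as SAP section 4.4.5.2 already prescribes.
- State that the difference in least squares means will be back-transformed and reported as an adjusted GMT ratio with its 95% CI.
- State that the adjusted group means are computed at the observed strata proportions. LSMEANS by default weights the levels of each factor equally. That would shift each adjusted GMT but not their ratio in the model without interaction.

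The cost is a few lines of SAP text and 3 df. Both factors are already in the data. If the strata explain nothing, the interval is about 0.1% wider.
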